After completing both baseline assessment appointments, families were randomly assigned to the music or control group. Families completed follow-up assessments using the same procedure after their first semester (8-week) and second semester (16-week). When possible, the same research staff ran appointments so that families remained familiar with the staff, especially the researcher who delivered the reinforcers to the infants. Lastly, we sent out a parent satisfaction survey via email to all enrolled families to assess the acceptability of the intervention.

Data Analysis Plan

Group baseline characteristics were compared using ANOVA or Pearson's chi-square test for frequency data. We performed an intention-to-treat analysis using all randomly assigned participants, including participants who dropped out of the program. The primary outcomes (RRV_{food} and home environmental enrichment measures) were analyzed with a mixed-model ANOVA, which handles missing data at random using maximum likelihood estimation and retains all randomly assigned subjects in the analysis. In an effort to choose a reasonably fitted model satisfying the model assumptions, the residual plots and the residual-based fit statistics, such as Akaike's Information Criterion, for various covariance structures were examined. The models included group, time (base- line, mid-, and post-intervention), and the group

× time interaction as class variables using the unstructured (UN) covariance structure. As a sensitivity analysis, we also performed repeated measures ANOVA for those who had complete data for all timepoints (i.e., the completers). Effect sizes were reported as partial eta squared for mixed model ANOVA, and eta-squares were converted to Cohen's f to ease model comparison. Effect sizes for repeated measures ANOVA similarly were computed from partial eta square and converted to Cohen's f using G*Power 3.1.9.6. Though p -values can inform whether an effect exists, Cohen's f can help to assess the strength of that effect and contextualize the results. Given the small sample size, we focus on interpreting group differences when there are medium (0.25) to large (0.4) effect size estimates. Since our study is a pilot study, knowing the expected effect size can inform power analyses for sample size determination of a future larger RCT. All models were performed using PROC MIXED in SAS version 9.4 (©2020, SAS Institute, Cary, NC, USA).

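### Cohen's f from a repeated-measures partial eta squared depends on the visit-to-visit correlation and the error df, so the 0.25 and 0.4 cut-offs do not measure the size of a group difference

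*Combined protocol and SAP*

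**What the plan says.** All the relevant text is in the Data Analysis Plan of the combined protocol and SAP.

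- The primary outcomes (RRV_food and the home enrichment measures) are analysed with group, time and their interaction. Time has three levels, "time (base- line, mid-, and post-intervention"), and the model enters the group by "time interaction as class variables using the unstructured (UN) covariance structure".
- For the main model: "Effect sizes were reported as partial eta squared for mixed model ANOVA, and eta-squares were converted to Cohen's f to ease model comparison".
- For the completers' sensitivity analysis: "Effect sizes for repeated measures ANOVA similarly were computed from partial eta square and converted to Cohen's f using G*Power 3.1.9.6". No conversion option is named.
- Use in interpretation: "Given the small sample size", the plan says, "we focus on interpreting group differences when there are medium (0.25) to large (0.4) effect size estimates".
- Use beyond the pilot: "knowing the expected effect size can inform power analyses for sample size determination of a future larger RCT".

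The plan does not say which model term f belongs to, how the denominator df are obtained, or what N, SD or visit-to-visit correlation applies. It names no mean difference and no confidence interval as an effect measure.

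**The concern.** The conventional 0.25 and 0.4 labels belong to f defined as the SD of the cell means divided by the within-cell SD. An f obtained from the partial eta squared of a within-family term has a different denominator: the within-family error, which shrinks as visits become more highly correlated. This is a matter of scale. It remains at infinite sample size and is separate from the imprecision of a small pilot.

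Two uses are at stake. First, f decides which group differences receive attention, so an outcome with high rho passes 0.25 with a smaller true difference than an outcome with low rho. The plan gives no reason to think that RRV_food and the home measures share one rho. The stated aim of easing comparison between models also fails if the mixed model and the completers' ANOVA use different error df. Second, f is offered as an input for sizing a later trial, without the quantities needed to translate it.

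**Working it through.** **Figures in the plan.** The only figures are the benchmarks. By eta_p² = f²/(1+f²), 0.25 corresponds to 0.0625/1.0625 = 0.059 and 0.4 to 0.16/1.16 = 0.138. The plan has no N or power to reproduce.

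**Inputs from the plan.** Three visits; two groups ("families were randomly assigned to the music or control group"); f converted from partial eta squared.

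**Assumed inputs.** 1:1 allocation, SD 1 at every visit, compound symmetry, group by time as the term, rho 0.3 to 0.8, and error df of either N-2 (a between-family df for the unstructured model) or 2(N-2) (univariate repeated-measures ANOVA).

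**Formula.** f = sqrt(eta_p²/(1-eta_p²)) = sqrt(F × df1/df_error), which for large N tends to sqrt(λ/df_error). With group differences δ_t at the three visits, λ = N Σ(δ_t - mean δ)² / [4(1-rho)].

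**Difference δ at both follow-ups (0, δ, δ).** The mean is 2δ/3, so Σ = (4/9 + 1/9 + 1/9)δ² = 2δ²/3 and λ = Nδ²/[6(1-rho)]. Hence:

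- error df N-2: f = δ/sqrt(6(1-rho))
- error df 2(N-2): f = δ/sqrt(12(1-rho))

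| δ = 0.5 | rho 0.3 | rho 0.5 | rho 0.7 |
|---|---|---|---|
| f, df N-2 | 0.244 | 0.289 | 0.373 |
| f, df 2(N-2) | 0.173 | 0.204 | 0.264 |
| δ behind f = 0.25, df N-2 | 0.51 | 0.43 | 0.34 |
| δ behind f = 0.25, df 2(N-2) | 0.72 | 0.61 | 0.47 |

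The two df conventions differ by sqrt(2) throughout.

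**A gradual pattern (0, 0.25, 0.5).** Here Σ = δ²/2, so f = δ/sqrt(8(1-rho)) or δ/sqrt(16(1-rho)). At rho 0.3, 0.5 and 0.8 this gives 0.211, 0.250 and 0.395 (df N-2), or 0.149, 0.177 and 0.280 (df 2(N-2)). Simulated medians at N = 400 were 0.220, 0.256 and 0.396, and 0.156, 0.180 and 0.281, close to these limits.

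**Group main effect.** Here f tends to (mean δ/2)/sqrt((1+2rho)/3). For 0, 0.5, 0.5 this is 0.228, 0.204 and 0.186 at rho 0.3, 0.5 and 0.7, so it falls as rho rises.

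**Carrying f = 0.25 to a later trial** (group by time test, rho 0.5, two-sided 0.05, 80% power, non-central F with 2 and 2(N-2) df):

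- Entered as SD-of-means/SD with rho applied again: λ = N × 3 × 0.0625/0.5 = 0.375N, giving a total of 28.
- Effect actually behind it, if f came with df 2(N-2): λ ≈ 0.0625 × 2N = 0.125N, giving 80. Power at 28 is 35%.
- Effect actually behind it, if f came with df N-2: λ ≈ 0.0625N, giving 156. Power at 28 is 19%.

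**When f does carry over.** For the gradual pattern at rho 0.3, 0.5 and 0.8, the same three-visit test needs 218, 156 and 64 in total. Using f with its own df convention and the same rho returns 220, 158 and 66 (df 2(N-2)) or 222, 160 and 68 (df N-2).

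**When the error can go either way.** For a two-arm comparison at the final visit with δ = 0.5, the need is 63 per arm. Reading the partial-eta-squared f as δ = 2f gives 177 per arm (f 0.149) or 26 per arm (f 0.395).

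**The case against.** The strongest reply is that nearly every input above is assumed. The plan says "group differences" without naming a term, and for the group main effect the error is between families and f moves the other way with rho. The df of N-2 is also an assumption. The 0.34 to 0.72 SD range belongs to one time pattern; the gradual pattern with the same rhos gives 0.39 to 0.84. The f supplements p-values in a small pilot and is not a success criterion. All of this stands, and it limits the figures to illustration. It does not rescue the cut-offs, because whichever term is meant, f depends on rho.

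A reader might infer three stronger conclusions that the documents do not support:

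- *That effects in this trial were mislabelled.* No rho, N, df method or term is given, so this cannot be shown.
- *That f is unusable for the later trial, or that the later trial will be undersized.* The plan says only that the effect size can inform power calculations and describes no later design or formula. With term, visits, rho and df convention matched, f recovers N to within about 4 families. With a mismatch, the error can go in either direction.
- *That the rule always flatters the effect.* This depends on the reference scale. A 0.5 SD difference at both follow-ups is f = sqrt((2 × 0.25/3)/12) = 0.118 as an interaction over all six cells, but a 0.5 SD difference at one visit is f = 0.5/2 = 0.25 as a two-group contrast. Labels could therefore move up or down.

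**Conclusion.** The point holds as a defect of the interpretation rule. Applied exactly as written, an f cut-off of 0.25 or 0.4 on a repeated-measures term does not measure the size of the group difference. Under the assumed inputs, one fixed difference of 0.5 SD at both follow-ups yields f anywhere from 0.17 to 0.37 across rho 0.3 to 0.7 and the two df conventions, and the df convention alone accounts for a factor of sqrt(2). The dependence on rho and df follows from algebra; the particular values rest on 1:1 allocation, equal variances, compound symmetry and the chosen time pattern.

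For the later trial, the supportable conclusion is conditional: f should not be carried over unless its term, visits, rho and df convention are known and match. The contrast of 28 with 80 or 156 arises only if f is entered as SD-of-means/SD and rho is applied a second time. The change is worth making before results are interpreted, but it does not invalidate the underlying models.

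**What to change.** - For each primary outcome, replace the f cut-offs as the interpretation rule with the model-based music-minus-control difference at 8 weeks and at 16 weeks, with 95% CI. Give it in the outcome's own units and divided by the pooled baseline SD, and judge size on that scale.
- Report the SD at each visit and the estimated correlations between visits as the inputs for the later trial.
- If f is kept, state its model term and df method. Do not read it against 0.25 and 0.4, and do not combine it with rho in a power formula as if it were SD-of-means/SD.

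The cost is a change of SAP wording and an ESTIMATE or LSMEANS statement per outcome in the PROC MIXED models already planned. No new data are needed. The downside is slightly more output, and some effects may change label in either direction.

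### Interpretation centres on an uncorrected Cohen's f of 0.25 or more because the sample is small, but in a small sample chance alone often produces an f of that size

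*Combined protocol and SAP*

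**What the plan says.** The Data Analysis Plan fits a mixed model with group, three timepoints and their interaction, under an unstructured covariance, to RRV_food and the home enrichment measures. A repeated measures ANOVA in completers is the sensitivity analysis.

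On effect sizes it says: "Effect sizes were reported as partial eta squared for mixed model ANOVA, and eta-squares were converted to Cohen's f to ease model comparison". For the completers: "Effect sizes for repeated measures ANOVA similarly were computed from partial eta square and converted to Cohen's f using G*Power 3.1.9.6".

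It assigns different roles to the two statistics, saying that p-values "can inform whether an effect exists, Cohen's f can help to assess the strength of that effect and contextualize the results". The rule for interpretation follows: "Given the small sample size, we focus on interpreting group differences when there are medium (0.25) to large (0.4) effect size estimates". The next sentence gives the pilot's purpose: "knowing the expected effect size can inform power analyses for sample size determination of a future larger RCT".

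The section states no sample size, alpha, confidence interval for f, small-sample correction, denominator-df method or formula for partial eta squared.

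**The concern.** The rule uses a small sample to justify relying on a point estimate that small samples inflate. Partial eta squared is zero or positive by construction, so pure noise yields a positive f, and a larger one as the sample shrinks.

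The rule also sits badly with the plan's own division of labour. If p-values inform whether an effect exists and f measures its strength, a cut-off on f alone does not require any evidence of an effect.

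Two things are at stake. Outcomes whose medium f is compatible with no effect may receive the emphasis in the report. And the same uncorrected f may feed the power calculation of a larger trial. The plan does not say that only estimates above the cut-off would be used there, but the uncorrected f is inflated even without selection.

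**Working it through.** The plan states no figure to reproduce, so this derives what the rule does when there is no true effect.

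**Inputs from the Data Analysis Plan:** two arms, three timepoints (group by time has 2 df), unstructured covariance, f taken from partial eta squared, lower benchmark 0.25 (f² = 0.0625).

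**Assumptions:** N = 20, 30, 40 or 60 families, complete data, 1:1 allocation; sphericity for the repeated measures ANOVA; REML-type variances and denominator df N-2 for the mixed-model interaction.

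**Formulas.** In general f² = η²/(1-η²) = F × df1/df2.

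- Group by time, unstructured: the test is of Hotelling type, with T² = 2(N-2)/(N-3) × F′ and F′ ~ F(2, N-3). So f² = T²/(N-2) = 2F′/(N-3), and P(f ≥ 0.25) = P[F(2, N-3) ≥ 0.0625(N-3)/2] = 1.0625^(-(N-3)/2). At N = 40 this is 1.0625^(-18.5) = 0.326.
- Group main effect: P[F(1, N-2) ≥ 0.0625(N-2)].
- Completers' repeated measures interaction: P[F(2, 2(N-2)) ≥ 0.0625(N-2)] = 1.0625^(-(N-2)).

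**Chance that f reaches 0.25 with no true effect, per outcome**

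| Effect | N=20 | N=30 | N=40 | N=60 |
|---|---|---|---|---|
| Group by time, unstructured | 59.7% | 44.1% | 32.6% | 17.8% |
| Group main effect | 30.3% | 19.7% | 13.2% | 6.2% |
| Completers' RM-ANOVA | 33.6% | 18.3% | 10.0% | 3.0% |

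Simulation of 40,000 trials per setting at N = 20, 40 and 60 agreed with these to within a percentage point. For the unstructured interaction the chance is 9.7% at N = 80 and 5.3% at N = 100. The same formula gives the p-value at an observed f of exactly 0.25: 0.33 at N = 40, first falling to 0.05 or below at N = 102.

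**What an observed f of 0.25 supports (unstructured interaction).** The 95% interval inverts the noncentral F with λ = f²(N-2). The corrected f uses ε² = 1-(1-η²)(N-1)/(N-3) with η² = 0.0625/1.0625 = 0.0588.

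| | N=20 | N=30 | N=40 | N=60 |
|---|---|---|---|---|
| 95% CI for f | 0 to 0.64 | 0 to 0.57 | 0 to 0.53 | 0 to 0.48 |
| ε² | -0.052 | -0.011 | 0.008 | 0.026 |
| Corrected f (negative ε² set to 0) | 0 | 0 | 0.09 | 0.16 |

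**Inflation at N = 40 (1,000,000 noncentral draws per true value)**

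| True f | Mean of all estimates | Mean of estimates ≥ 0.25 |
|---|---|---|
| 0.15 | 0.25 | 0.37 |
| 0.25 | 0.32 | 0.40 |
| 0.40 | 0.45 | 0.48 |

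**Consequence for a larger trial.** Take a true f of 0.15, two-df unstructured test, alpha 0.05 and 80% power. The trial needs about 434 families. Sizing on the average unselected estimate (0.25) gives about 160, with true power 37%. Sizing on the average selected estimate (0.367) gives about 78 under equal allocation, with true power 19%.

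**The case against.** The strongest objection concerns denominator degrees of freedom. The plan does not say how partial eta squared is obtained from PROC MIXED, and the interaction figures take the denominator as N-2. If the same F were converted with 2(N-2), f² would be halved. The chance of reaching 0.25 would then be 1.125^(-(N-3)/2), or 37%, 20%, 11% and 3.5% at the four sample sizes. N-2 is the between-family df and fits an unstructured, Hotelling-type test, but the convention is an assumption. The intervals, corrected values, inflation means and trial sizes above share it. The alternative lands close to the repeated measures range, so it lowers the size of the interaction problem without removing it.

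Second, the sample size is assumed. This stands: the figures are a range, the problem is minor by 80 to 100 families, and the plan does not say which effect it means by a group difference. The direction of the bias does not depend on any of this.

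Third, the wording is soft. The plan speaks of focus, keeps p-values, and says only that the effect size may inform a later power analysis. That is fair, and nothing says that smaller effects go unreported. But the focus is not conditional on p, so a result with p = 0.33 at N = 40 qualifies for emphasis.

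Fourth, emphasis on effect sizes is common in a pilot, and intervals plus a bias correction would repair much of the problem. That is true. The advice on sizing the larger trial is separable, and the rest of the fix stands without it.

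**Conclusion.** The concern holds and should be fixed. With no true effect and 20 to 60 families, an f of at least 0.25 arises in 60% to 18% of trials for the unstructured interaction, 30% to 6% for the group main effect and 34% to 3% for the completers' analysis. Confidence is high in the direction. The size depends on the assumed sample size and complete data, on sphericity for the completers' analysis, and on the N-2 convention for the interaction.

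Other departures mostly raise the rates. ML in place of REML variances gives 63% to 19% for the interaction. Dropout reduces the number of completers (43% at 16). With several primary measures, the chance that at least one reaches 0.25 is higher than any single figure. The loss of power in a later trial is an illustration at a true f of 0.15; at a true f of 0.40 the average estimate is 0.45, a modest bias.

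**What to change.** Remove the 0.25/0.4 benchmarks as the basis for interpretation. For every primary outcome, whatever the size of its estimate, report the music-minus-control differences in change from baseline at 8 and at 16 weeks from the planned mixed model, with 95% confidence intervals, and interpret the intervals.

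If f is kept, give a bias-corrected version (omega- or epsilon-squared) with its confidence interval, and state the denominator df and the formula used.

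Do not size the larger trial on the uncorrected f or on estimates chosen for being large. Use the pilot's SD, repeated-measures correlation and attrition, together with a separately justified minimum worthwhile difference.

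The cost is revised wording and a few ESTIMATE or LSMEANS lines from a model already planned. The plan is written in the past tense, so this may now be a change to reporting, and it needs no new data. The price is that intervals will be wide, fewer results will look noteworthy, and the minimum worthwhile difference needs its own justification.

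### The f 0.25/0.4 rule names no model term; if it is applied to the group main effect, that term averages in the pre-randomisation visit and understates the program effect

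*Combined protocol and SAP*

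**What the plan says.** The Study Protocol places randomisation after baseline: "After completing both baseline assessment appointments, families were randomly assigned to the music or control group". Two follow-ups come later: "Families completed follow-up assessments using the same procedure after their first semester (8-week) and second semester (16-week").

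The Data Analysis Plan makes baseline one of three levels of time and fits group as a term of its own: "The models included group, time (base- line, mid-, and post-intervention), and the group" by "time interaction as class variables using the unstructured (UN) covariance structure". On effect sizes it says: "Effect sizes were reported as partial eta squared for mixed model ANOVA, and eta-squares were converted to Cohen's f to ease model comparison". The rule for what gets interpreted is: "we focus on interpreting group differences when there are medium (0.25) to large (0.4) effect size estimates". Their later use is also stated: "knowing the expected effect size can inform power analyses for sample size determination of a future larger RCT".

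The plan does not say whether the rule refers to the group main effect, the group by time interaction or a contrast at follow-up. It specifies no follow-up-only or baseline-adjusted contrast.

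**The concern.** In a model with group, time and their interaction, the group main effect is the equally weighted mean of the arm differences at the three visits. One of those visits precedes randomisation, so the program cannot have affected it. A third of the average therefore contributes no effect, only chance imbalance.

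Group is one of the three listed terms, and a reader could naturally take an arm difference to mean that term. Two things follow if it is used. A sustained effect is shrunk before it is compared with 0.25, so it may be passed over. The f handed to the larger trial is also too small. The plan relies on effect-size marks because the sample is small, so the choice of term determines what is reported.

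**Working it through.** **Inputs.** From the documents: three visits, baseline before randomisation, the three model terms, and the marks of 0.25 and 0.40. The documents give no sample size, SD or between-visit correlation, and no design figure to reproduce. Assumed: unit variance at each visit, complete data, equal arms, a common correlation r between visits, and the same effect D (in SD units) at weeks 8 and 16.

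**Step 1: raw scale.** Write d0, d8 and d16 for the arm differences at the three visits. The group term is (d0 + d8 + d16)/3. Randomisation gives d0 an expectation of 0, so the expected value is (0 + D + D)/3 = 0.667 D. If the week 8 effect is half the week 16 effect, the term is (0 + 0.5 + 1)/3 = 0.50 of the week 16 effect, which is still two thirds of the follow-up mean (0.50/0.75).

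**Step 2: f scale.** For two equal arms, f = effect / (2 × SD of the per-family summary).

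- Group term: effect 2D/3, variance (1 + 2r)/3.
- Plain mean of weeks 8 and 16: effect D, variance (1 + r)/2.
- The same mean adjusted for baseline: effect D, variance (1 + r)/2 − r².

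The ratio of group-term f to plain follow-up f is (2/3) × √{[(1 + r)/2] / [(1 + 2r)/3]}. It is 0.816 at r = 0, 0.707 at r = 0.5 and 0.673 at r = 0.9, which are losses of 18%, 29% and 33%. For D = 0.5:

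| r | f, group term | f, plain follow-up mean | f, baseline-adjusted | Loss v plain | Loss v adjusted |
|---|---|---|---|---|---|
| 0.3 | 0.23 | 0.31 | 0.33 | 26% | 32% |
| 0.5 | 0.20 | 0.29 | 0.35 | 29% | 42% |
| 0.7 | 0.19 | 0.27 | 0.42 | 31% | 55% |

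At r = 0.5, for example, the group term gives 0.333 / (2 × √0.667) = 0.20 and the adjusted mean gives 0.5 / (2 × √0.5) = 0.35. For the group-term f to reach 0.25, the true effect must be 0.55, 0.61 or 0.67 SD at r = 0.3, 0.5 or 0.7.

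**Step 3: share of variance due to baseline.** The share of the group term's sampling variance explained by d0 is Cov² / (Var × Var) = (1 + 2r)/3. This is 33% at r = 0, 47% at 0.2, 50% at 0.25, 67% at 0.5 and 80% at 0.7. Under AR(1) correlation it is 33% at 0, about 50% at 0.4, 56% at 0.5 and 71% at 0.7. These shares include what baseline carries through its correlation with the follow-ups.

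**Step 4: no true effect.** An estimated f of 0.25 corresponds to F = 0.25² × error df. At an assumed 15 per arm this is 0.0625 × 28 = 1.75. In simulation (20,000 trials, r = 0.5) the group term reached the mark in 19% of trials: 38% when the baseline difference exceeded 0.3 SD and 6% when it did not.

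**Step 5: the future trial.** Required sample size varies as 1/f². At r = 0.5, planning a trial on the follow-up mean from the group-term f would inflate its size by 1/0.707² = 2.0. For a baseline-adjusted analysis the factor is 1/0.577² = 3.0.

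**The case against.** **The plan does not say it uses this term.** That is correct. The interaction is the usual treatment term in such a model, and it is not diluted in this way. A reader might infer that the interpreted differences do include the main effect. The text supports only that the term is unnamed and the main effect is not excluded, so everything above is conditional on its use.

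**False positives are not more frequent.** This also stands. With no effect, the chance that f reaches 0.25 is about 20% at 15 per arm for any single-df contrast between families, including the one proposed below. The 38% against 6% shows which trials cross the mark, not that more do. A reader might infer an inflated error rate, and that would be wrong.

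**Part of the gain is covariate adjustment.** At an assumed 40 families in total, D = 0.5 and r = 0.7, power is 21% for the group term, 39% for the plain follow-up mean and 73% for the adjusted mean. Of the 52-point gap, 18 points come from dropping baseline from the average and 34, about two thirds, from adjustment. Both comparisons are therefore shown above.

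**Two stronger statements hold only in part.** One is that a 0.5 SD effect always falls below 0.25. At r = 0.1 the group-term f is 0.26, and estimates scatter: with 40 families they reach 0.25 in about 47%, 41% and 37% of trials at r = 0.3, 0.5 and 0.7. The other is that baseline imbalance drives most of the term's variation, which fails below r = 0.25 (or about 0.4 under AR(1)). The documents give no correlation that would settle either.

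**For a pilot this is a small clarification.** The change is small. But naming a term is not enough if the term named is the main effect, and supplying an effect size for a later trial is a stated purpose of this pilot.

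**Conclusion.** The point holds in conditional form. The rule names no term, and one of the terms it could refer to is not a treatment effect in this model.

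If the group main effect is used, the raw-scale loss is exactly one third for an effect equal at both follow-ups, and that result does not depend on the correlation. The f-scale losses and the baseline shares do depend on it. They assume equal variances, complete data and the stated correlation pattern. Chance imbalance accounts for at least a third of the term's variance when correlations are not negative, and for more than half only above the correlations given. The firmest consequence is for the larger trial: an f from this term understates the effect.

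**What to change.** Add a sentence stating that the group main effect of the three-visit model is not interpreted, not compared with 0.25 or 0.4, and not carried to the future trial.

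Refit in PROC MIXED as a constrained longitudinal model: three visits as outcomes, unstructured covariance, baseline means set equal across arms, and separate arm differences at weeks 8 and 16. From that model, use an ESTIMATE statement to give the average of the two follow-up differences with its 95% CI, and base the effect size on it. State that this effect size is baseline-adjusted, so that the later trial is planned on the same footing.

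An ESTIMATE statement in the present model would not do this. With baseline means free in each arm, it yields raw visit averages or changes, not a contrast given baseline. Moving baseline to a covariate with only follow-up outcomes would drop families who have no follow-up, against the plan's aim of keeping everyone randomised. The constrained model keeps them.

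The cost is one refit and one sentence, using data and software already in the plan.
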